9.2.3 Secondary endpoint(s) analyses

9.2.3.1 Key Secondary Endpoints

VGPR or better rate per IRC assessment will be summarized for the ITT population in the same way as for ORR endpoint. The non-inferiority test for non-unity null according to Farrington and Manning (1990) will be performed for VGPR or better rate. The non-inferiority margin is 0.6312 which was calculated as 40% retention of the observed historical clinical benefit of VGPR or better ratio 0.478 (upper bound of the 95% CI of rate ratio for Pd over CD38+ Pd as demonstrated in ICARIA-MM trial) under the logarithm scale then converting back to its original scale. If the lower bound of the 95% CI is not less than a non-inferiority margin of 0.6312, the non-inferiority of Isa-SC + Pd relative to Isa- IV + Pd on the VGPR or better rate will be concluded.

The PK endpoint of CT4W will be summarized for the CT4W-PK population in the same way as for the C_{trough} at steady state endpoint. The non-inferiority of Isa- SC + Pd relative to Isa-IV + Pd on CT4W corresponding to predose at C2D1 will be concluded if the lower bound of the 90% CI for the geometric mean ratio of CT4W is at least 80% (a non-inferiority margin of 80%).

Incidence rate of IRs will be compared between treatment arms on the safety population using the Fisher's exact test. The relative risk, odds ratio of ISA- SC+ Pd relative to Isa- IV + Pd with their 95% CI will be provided.

Percentage of participants who reported satisfied or very satisfied with the injection method used to administer the study medication based on the PESQ questionnaire at C5D15 visit will be compared between treatment arms on the ITT population using the stratified CMH method.

9.2.3.2 Other Secondary Endpoints

The CR rate will be summarized in the same way as for ORR endpoint.

The median PFS per IRC assessment and probabilities of being progression free at different time points calculated using the Kaplan-Meier methods as well as corresponding 95% CI will be presented by treatment arm. The Kaplan-Meier PFS curves will also be provided. Additionally, the HR estimated from the Cox proportional hazards model as well as its associated 95% CI will be provided too.

The analysis for PFS2, OS, DOR, and TTR (TT1R and TTBR) as well as the impact of abnormal cytogenetic subtypes will be similar to that described for PFS per IRC assessment.

PK parameters and derived exposure will be summarized and provided in a separate report. PK concentrations (C_{trough} and C_{eo1} - Isa-IV+Pd arm for C_{eo1} only) will be summarized per arm with descriptive statistics.

Incidence of participants with ADA against isatuximab will be provided in a separate table.

Number (and percentage) of participants experiencing TEAEs by primary system organ class and preferred term will be summarized by NCI CTCAE (v5.0) grade (all grades and \geq Grade 3) for the safety population. The same summaries will be prepared for treatment related TEAEs, TEAEs leading to treatment discontinuation, TEAEs leading to dose modification, serious TEAEs and TEAEs with fatal outcome and ISRs. Second primary malignancies as AESI will be reported throughout the study.

Hematology and biochemistry results will be graded according to NCI CTCAE v5.0. Number (and percentage) of participants with laboratory abnormalities (ie, all grades and \geq Grade 3) using the worst grade during the on-treatment period will be provided for the safety population.

Number of successful injections with investigational isatuximab injector device will be assessed.

Participant expectations at baseline, participant experience, and satisfaction, assessment of treatment, and Health Resource Utilization and Productivity questionnaires will be descriptively summarized.

Participants' health-related quality of life (influenced by both disease and treatment) will be assessed by EORTC QLQ-C30 and EORTC QLQ-MY20 via a comparison of change scores in C30 (individual symptom change scores) and MY20 (disease- and treatment-related summary scores) from baseline to follow-up between treatment arms. In addition, responder analyses will be conducted 1) for those who improve and 2) for those who deteriorate, utilizing the CIDs for all individual symptom scores (C30) and disease- and treatment-related summary scores (MY20) for both treatment arms.

Health status (EQ-5D-5L, including VAS) will be assessed via a comparison of EQ-5D-5L health status change scores from baseline to follow-up between treatment arms. In addition, responder analyses will be conducted 1) for those who improve and 2) for those who deteriorate, utilizing the CIDs for health status VAS scores for both treatment arms.

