Secondary	
Key Secondary
 
• Demonstrate the efficacy non-inferiority between isatuximab SC and isatuximab IV in combination with Pd.• Demonstrate the PK non-inferiority between isatuximab SC and isatuximab IV in combination with Pd.• Assess safety of isatuximab SC and IV in combination with Pd.• Assess patient satisfaction with isatuximab SC and IV. 
Other Secondary
 
• Assess efficacy of isatuximab SC compared to isatuximab IV in combination with Pd.	
• Very Good Partial Response or better rate: defined as the proportion of participants with sCR, CR, and VGPR according to the 2016 International Myeloma Working Group (IMWG) criteria assessed by IRC.• Observed concentration before dosing (C_{trough}) at 4 weeks (ie, CT4W corresponding to predose at C2D1).• Incidence rate of infusion-reactions (IRs).• Percentage of participants satisfied or very satisfied with the injection method used to administer study medication based on the patient experience and satisfaction questionnaire (PESQ).• Duration of response (DOR): defined as the time from the date of the first response to the date of first occurrence of progressive disease (PD) as determined by IRC or death from any cause, whichever happens first. DOR is determined only for participants who have achieved a response (PR or better). In the absence of PD or death before the analysis cut-off date, the DOR will be censored at the date of the last valid disease assessment performed prior to initiation of a further anti-myeloma treatment or the analysis cut-off date, whichever is earlier. Patients with two or more consecutive missed assessments prior to PD or death will be censored at the last valid disease assessment. Details about censoring rule will be provided in statistical analysis plan (SAP).• Time to first response (TT1R): defined as the time from randomization to the date of first IRC determined response (PR or better) that is subsequently confirmed. Details about censoring rule will be provided in SAP.

Objectives	Endpoints

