
Assess safety of isatuximab SC and IV and local tolerability of isatuximab SC in combination with Pd.Characterize PK of isatuximab SC and IV in combination with Pd.Assess the delivery performance of the (investigational) device injector.Assess the potential immunogenicity of isatuximab SC and IV in combination with Pd.	
Time to best response (TTBR): defined as the time from randomization to the date of first occurrence of IRC determined best overall response (PR or better) that is subsequently confirmed. Details about censoring rule will be provided in SAP.Progression free survival (PFS): defined as the time from the date of randomization to the date of first documentation of PD as determined by IRC or the date of death from any cause, whichever comes first. Responses will be determined according to IMWG criteria. Progression based on paraprotein will be confirmed based on two consecutive assessments. PFS will be censored at the date of the last valid disease assessment not showing disease progression performed prior to initiation of a further anti-myeloma treatment (if any) or the analysis cut-off date, whichever comes first. Patients with two or more consecutive missed assessments prior to PD or death will be censored at the last valid disease assessment. Details censoring rule will be provided in the SAP.Overall survival (OS): defined as the time from the date of randomization to death from any cause. Participants without death prior to the analysis cut-off date will be censored at the last date the participant was known to be alive or the cut-off date, whichever is first. Details censoring rule will be provided in SAP.PFS2: defined as time from the date of randomization to the date of first documentation of PD (as assessed by investigator) after initiation of further anti-myeloma treatment or death from any cause, whichever happens first. Same censoring rule applies as in the PFS endpoint.Treatment-emergent adverse events (TEAEs)/serious adverse events (SAEs). Treatment-emergent adverse events (TEAEs) are defined as adverse events (AEs) that develop, worsen (according to the Investigator opinion), or become serious during the treatment period. The treatment period is defined as the time from first dose of study treatment up to 30 days after last dose of study treatment.Laboratory parameters.Injection site reactions (ISRs) – SC arm only.Adverse events and laboratory parameters will be graded using NCI CTCAE v5.0.PK concentrations.Number of successful injections with (investigational) isatuximab injector device defined as completion of administration per provided instructions for use with no use errors or technical issues, divided by the total number of injections.Incidence of participants with anti-drug antibodies (ADA) against isatuximab

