A total sample size of 534 participants (randomization ratio 1:1, ie, 267 randomized participants in the SC arm, and 267 randomized participants in the IV arm) was determined to demonstrate non-inferiority of SC arm versus IV arm on the proportion ratio of participants who achieved ORR, and the geometric mean ratio of C_{trough} at steady state (corresponding to predose at C6D1). For the co-primary efficacy endpoint of ORR, the non-inferiority test for non-unity null according to Farrington and Manning (1990) was implemented. With 2.5% one sided Type I error rate, and a non-inferiority margin of 0.839 which was calculated as 40% retention of the observed historical clinical benefit of ORR ratio 0.7463 (upper bound of the 95% confidence interval [CI] of rate ratio for Pd over CD38+ Pd as demonstrated in ICARIA-MM trial) under the logarithm scale then converting back to its original scale, 534 randomized participants provide approximately 80% power for this efficacy co-primary endpoint assuming that ORR for IV arm is 60.4% and the true response rate is 1.02 for SC arm over IV arm. For the PK co-primary endpoint of C_{trough} at steady state (corresponding to predose at C6D1), assuming C_{trough} at steady state follows log normal distribution with a true geometric mean ratio of 1, and a CV of 75%, and an assumed drop-out rate of no more than 50% to the PK per-protocol population, 534 randomized participants will provide at least 86% power to show the lower bound of the 90% CI of the geometric mean ratio of C_{trough} at steady state is at least 80% (a non-inferiority margin of 80%). Calculations were made based on SAS 9.4 (1).

Main analysis populations

Intent-to-treat (ITT) population

The ITT population is the randomized population. All participants who have given their informed consent and for whom there is confirmation of successful allocation of a randomization number by the IRT will be included in this population. Participants will be analyzed according to the treatment group allocated by IRT, regardless of whether the participants received any study treatment or received a different study treatment from that to which they were randomized.

This population will be used for the analysis of the co-primary efficacy endpoint.

All efficacy analyses will be performed on this population.

Safety Population

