If the co-primary endpoints are significant, the key secondary endpoints will be tested by hierarchical testing in the order of VGPR or better rate, CT4W, incidence rate of IRs, and the percentage of participants who reported satisfied or very satisfied with the injection method used to administer the study medication.

VGPR or better rate per IRC will be summarized for the ITT population in the same way as for ORR endpoint. The non-inferiority test for non-unity null according to Farrington and Manning (1990) will be performed for VGPR or better rate. The non-inferiority margin is 0.6312 which was calculated as 40% retention of the observed historical clinical benefit of VGPR or better ratio 0.478 (upper bound of the 95% CI of rate ratio for Pd over CD38+ Pd as demonstrated in ICARIA-MM trial) under the logarithm scale then converting back to its original scale. If the lower bound of the 95% CI is not less than a non-inferiority margin of 0.6312, the non-inferiority of Isa-SC + Pd relative to Isa- IV + Pd on the VGPR or better rate will be concluded.

The PK endpoint of CT4W will be summarized for the PP-PK population for CT4W in the same way as for the C_{trough} at steady state endpoint. The non-inferiority of Isa- SC + Pd relative to Isa-IV + Pd on CT4W will be concluded if the lower bound of the 90% CI for the geometric mean ratio of CT4W is at least 80% (a non-inferiority margin of 80%).

Incidence rate of IRs will be compared between treatment arms on the safety population using the Fisher's exact test. The relative risk, odds ratio of ISA- SC+ Pd relative to Isa- IV + Pd with their 95% CI will be provided.

Percentage of participants who reported satisfied or very satisfied with the injection method used to administer the study medication based on the PESQ at C5D15 visit will be compared between treatment arms on the ITT population using the stratified Cochran–Mantel–Haenszel (CMH) method.

Analysis of other secondary endpoints

The median PFS per IRC assessment and probabilities of being progression free at different time points calculated using the Kaplan-Meier methods as well as corresponding 95% CI will be presented by treatment arm. The Kaplan-Meier PFS curves will also be provided. The Hazard Ratio (HR) estimated from the Cox proportional hazards model as well as its associated 95% CI will be provided too.

The analysis for PFS2, OS, DOR, and time-to-response (TTR) will be similar to that described for PFS per IRC assessment.

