
Secondary
 
Key Secondary
 
• Assess efficacy of isatuximab SC compared to isatuximab IV in combination with Pd.• Demonstrate the pharmacokinetic (PK) non-inferiority between isatuximab SC and isatuximab IV in combination with Pd.• Assess safety of isatuximab SC and IV in combination with Pd.• Assess patient satisfaction with isatuximab SC and IV. 
Other Secondary
 
• Assess efficacy of isatuximab SC compared to isatuximab IV in combination with Pd.	
• Very Good Partial Response or better rate: defined as the proportion of participants with sCR, CR, and VGPR according to the 2016 International Myeloma Working Group (IMWG) criteria assessed by IRC.• Observed concentration before dosing (C_{trough}) at 4 weeks (ie, CT4W corresponding to predose at C2D1).• Incidence rate of infusion-reactions (IRs).• Percentage of participants satisfied or very satisfied with the injection method used to administer study medication based on the PESQ questionnaire.• Duration of response (DOR): defined as the time from the date of the first response to the date of first occurrence of progressive disease (PD) as determined by IRC or death from any cause, whichever happens first. DOR is determined only for participants who have achieved a response (PR or better). In the absence of PD or death before the analysis cut-off date, the DOR will be censored at the date of the last valid disease assessment performed prior to initiation of a further anti-myeloma treatment or the analysis cut-off date, whichever is earlier. Patients with two or more consecutive missed assessments prior to PD or death will be censored at the last valid disease assessment.• Time to first response (TT1R): defined as the time from randomization to the date of first IRC determined response (PR or better) that is subsequently confirmed.

Objectives	Endpoints

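### The PFS-type Kaplan-Meier template is a poor fit for TT1R and TTBR: if its censoring rule is carried over, it will overstate the probability of response

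*Protocol*

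**What the plan says.** Section 9.2.3.2 sets out the PFS analysis: Kaplan-Meier medians and curves by arm, "probabilities of being progression free at different time points calculated using the Kaplan-Meier methods as well as corresponding 95% CI", and a Cox hazard ratio. It then extends that method: "The analysis for PFS2, OS, DOR, and TTR (TT1R and TTBR) as well as the impact of abnormal cytogenetic subtypes will be similar". The synopsis (Section 1.1) has the same instruction: "The analysis for PFS2, OS, DOR, and time-to-response (TTR) will be similar to that described for PFS per IRC assessment".

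Both response-time endpoints start at randomisation. TT1R is "defined as the time from randomization to the date of first IRC determined response (PR or better) that is subsequently confirmed". TTBR is "defined as the time from randomization to the date of first occurrence of IRC determined best overall response (PR or better"). Neither is limited to responders, whereas for duration of response the synopsis says "DOR is determined only for participants who have achieved a response (PR or better"). Of the ITT population the synopsis says: "All efficacy analyses will be performed on this population".

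The synopsis leaves the censoring rule to the SAP, separately for TT1R and TTBR. For PFS it gives a rule: censor at the last valid disease assessment before further anti-myeloma therapy or the cut-off, whichever is earlier.

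**The concern.** In PFS, progression and death are the event. In TT1R and TTBR they cannot be, and for a participant who has not responded they end the chance of a countable response. They are therefore competing events. Kaplan-Meier has no place for a competing event except as censoring. Censoring at or near its date assumes that the participant would have gone on to respond at the same rate as those still at risk.

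The method to which the protocol points leads towards that rule. Section 8.2 and footnote bb of the schedule of activities run the myeloma laboratory tests up to progression. Afterwards Section 4.5 follows participants every 3 months for further therapy, second malignancies, PFS2 and survival. The last valid assessment of a progressing non-responder therefore falls at about progression.

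The result would also sit badly with the co-primary endpoint. Table 7 counts anyone without a confirmed PR as a non-responder, whatever the reason. A censored Kaplan-Meier curve would treat the same people as still able to respond, so one report could show a response probability above its own ORR.

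**Working it through.** **Inputs from the protocol.** ORR 60.4% and 267 per arm (Section 9.5); IsaPd median PFS 11.53 months in the earlier Phase 3 trial (Section 2.2.3.1); 28-day cycles with disease laboratory tests on Day 1 of each. The protocol gives no figure for TT1R or TTBR. As a check on the planning inputs, a Farrington-Manning calculation with 267 per arm, 60.4%, ratio 1.02, margin 0.839 and one-sided 0.025 returns 80.05% power, against the stated 80% or so.

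**Assumptions not in the protocol.** Median time to response among responders 1, 2 or 3 months, observed on a 28-day grid; responder median PFS m_R of 15, 18 or 22 months; follow-up spread evenly from 6 to 24 months.

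**Non-responder progression.** With exponential times, the mixture must give 50% progression-free at 11.53 months:

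S_N = (0.5 − 0.604 × 0.5^(11.53/m_R)) / 0.396, and m_N = 11.53 × ln 2 / (−ln S_N).

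For m_R = 18: 0.5^(11.53/18) = 0.6415; S_N = (0.5 − 0.3875)/0.396 = 0.284; m_N = 6.35 months. For m_R = 15 and 22, m_N is 7.98 and 5.00 months.

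**The mechanism in closed form.** With constant hazards, a total hazard λ and 60.4% of it for response, the cumulative incidence is 0.604(1 − e^(−λt)), while one minus Kaplan-Meier with competing events censored is 1 − e^(−0.604λt). If half of all participants have responded, progressed or died by 2 months, λ = ln 2/2 = 0.347. At 6 months the two are 0.604 × 0.875 = 0.528 and 1 − 0.125^0.604 = 0.715.

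**Simulation** (400,000 participants per scenario, non-responders censored at progression or death). Ranges run over m_N from 7.98 down to 5.00 months.

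| Median time to response, responders (months) | Excess of 1−KM at 6 months (points) | Excess at 12 months (points) | Overall median: true, then Kaplan-Meier (months) |
|---|---|---|---|
| 1 | 5.1 to 8.2 | 5.9 to 9.7 | 2.76, 2.76 |
| 2 | 5.4 to 8.5 | 9.8 to 15.9 | 5.52, 4.60 |
| 3 | 4.7 to 7.4 | 11.0 to 17.2 | 8.28, 5.52 to 6.44 |

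For example, with a 2-month response median and m_N = 6.35, the 12-month value is 71.8% against a true 59.4%. The standard error at 267 per arm is 3.1 to 3.8 points.

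**Wider inputs.** With a lognormal response time (median 1.5 months) and non-responder medians from 12 down to 2 months, one minus Kaplan-Meier is 62% to 79% against 59% at 6 months, and 64% to 86% against 60% at 12 months.

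**Same data, other censoring rule.** With non-responders kept at risk to the data cut-off, the excess is zero in every scenario.

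**Between arms.** Take two arms with identical response (2-month median) but non-responder medians of 8 and 4 months, both assumed. At 12 months one minus Kaplan-Meier is 69% and 79%: a spurious 10-point advantage for the arm that progresses faster. With equal progression the excess is the same in both arms.

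**The case against.** The strongest reply is that the censoring rule decides everything and the protocol has not set it. Section 9.2 describes itself as a summary, the method is called similar to that for PFS rather than identical, and an SAP rule that keeps non-responders at risk to the cut-off is compatible with the wording and removes the bias. That stands. A reader might infer from Section 9.2.3.2 that the response probabilities are already bound to be overstated; the protocol does not support that.

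Two other strong readings also fail. One is that the median time to response will be too early: with a 1-month response median it does not move at all. The other is that the comparison of SC with IV is distorted: that needs different early progression in the two arms, and nothing in the protocol predicts it. The planning ratio for response is 1.02. A Cox hazard ratio from data censored at progression or death is also a legitimate quantity, provided that it is read as cause-specific.

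The inputs are soft too. The 11.53 months comes from a trial that required at least two prior lines, while this one admits participants after one, and the response times are assumed.

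What remains is that the protocol defers only the censoring details. It does name the template, and the censoring rule written for that template is the one that produces the bias. The unbiased rule departs from it.

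**Conclusion.** The point holds in conditional form. PFS is a poor template for TT1R and TTBR, because progression or death without response is a common competing event. If the SAP inherits PFS censoring, one minus Kaplan-Meier will exceed the true cumulative incidence of response by about 5 to 8.5 points at 6 months and 6 to 17 points at 12 months under the assumptions above. By 12 months it will also exceed the trial's own ORR. If the SAP keeps non-responders at risk to the cut-off, there is no bias.

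The consequence is small. Section 9.2.5 does not place either endpoint in the testing hierarchy, and ORR reports the proportion of responders correctly in the same ITT population. No confirmatory conclusion, error rate or sample size is affected. This is a minor improvement at almost no cost.

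**What to change.** In Sections 1.1 and 9.2.3.2, remove TT1R and TTBR from the sentence that refers to the PFS method. Instead:

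- Report the cumulative incidence of first and of best response in ITT (Aalen-Johansen), with progression, death and start of further anti-myeloma therapy without response as competing events. Keeping such participants at risk to the data cut-off in a Kaplan-Meier analysis serves the same purpose.
- Add the median and range of time to response among responders, labelled descriptive.
- If a Cox hazard ratio from data censored at progression or death is kept, label it cause-specific.

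The cost is one sentence in each of the two sections and a matching rule in the SAP. The data are already collected and the procedure is standard.
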